### 16. PUBLICATIONS

Refer to the Clinical Trial Agreement for information regarding JJV publication policies.

### 17. RISK ANALYSIS

#### POTENTIAL RISKS AND RISK MANAGEMENT

##### *RISKS OF THE TECNIS NEXT-GENERATION IOLS, MODELS ZFR00 AND ZYR00*

The TECNIS Models ZFR00 and ZYR00 IOLs are designed to provide far, intermediate and near vision; however, glasses may still be needed to improve distance vision and/or to have useful vision for intermediate or near tasks. Visual symptoms, particularly dysphotopsias such as halos, night glare, starbursts, etc., are expected to be comparable to or less than with a standard multifocal IOL. Dysphotopsias may become less noticeable over time; however, the IOL may be removed if necessary. There may be a reduction in contrast sensitivity under certain conditions compared to a monofocal lens although contrast sensitivity is expected to be in between that of the TECNIS Symphony IOL and TECNIS Multifocal IOLs. Due to the diffractive optic design, the ability to perform some eye treatments (e.g., retinal photocoagulation) may be affected, and caution should be used when interpreting results of autorefractors or wavefront aberrometers that utilize infrared light, or when performing a duochrome test. These risks are not unlike other diffractive technology IOLs.

##### *GENERAL RISKS OF CATARACT SURGERY AND IOL IMPLANTATION*

There are risks and complications associated with cataract surgery and IOL implantation in general. These can include worsening of vision, hemorrhage, loss of corneal clarity, inflammation, infections, retinal detachment, pupil changes, glaucoma, etc. Complications can result in poor vision, loss of vision or loss of the eye.

##### *RISK MANAGEMENT*

Subjects will be closely monitored throughout the trial duration. The occurrence of adverse events and complaints will be assessed at each study visit and reported to JJV

according to Section 11.0, Adverse Events and Product Complaints. Additionally, JJV will monitor incoming data following the procedures outlined in Section 15.0, Monitoring. The Medical Monitor will ensure subjects are not exposed to additional risks by monitoring serious adverse events, device-related adverse events, and device-deficiencies that could have led to serious adverse events (Section 15.3, Safety Monitoring).

### POTENTIAL BENEFITS

The general clinical performance of the TECNIS Next-Generation IOLs, Models ZFR00 and ZYR00, are expected to be similar to the TECNIS Model ZLB00 control IOL regarding distance and near visual acuities and safety outcomes. Improved intermediate visual acuity and functionality may be achieved with the TECNIS Next-Generation IOLs, Models ZFR00 and ZYR00 with comparable or less levels of dysphotopsia as compared to the control IOL.

### CONCLUSION

The hazards/risks associated with the TECNIS Next-Generation IOLs, Models ZFR00 and ZYR00, are acceptable and within those of JJV's other advanced optic IOLs. The potential clinical benefits of the TECNIS Next-Generation IOLs, Models ZFR00 and ZYR00, outweigh the residual risks when the device is used as intended.

## **18. RECORDS RETENTION**

All study-related correspondence, subject records, consent forms, Authorization for Use/Disclosure of Health Information Forms or similar medical treatment privacy law documentation, records of the distribution and use of all study products, and original case report forms should be maintained by the investigator.

The investigator must maintain and have access to the following essential documents until notified by the Sponsor. Note: This may be for a minimum of 25 years after completion of the study. JJV requires notification if the investigator wishes to relinquish ownership of the data so that mutually agreed-upon arrangements can be made for transfer of ownership to a suitably-qualified, responsible person.

- All case report forms
- All adverse event information (i.e., medical records, medical reports and/or judgments from colleagues or outside specialists who assisted in the treatment and follow-up of the subject)
- Investigational supply records/inventory
- IRB approval documentation
- Study correspondence
- Study agreements

- Site visit documentation
- Protocol(s)
- Subject log(s)
- Clinical Investigator's Brochure
- Completed subject informed consent forms and medical privacy forms (e.g., Authorization for Use/Disclosure of Health information)
- Subject medical chart/clinic notes (Not applicable for transfer of ownership to JJV)

## **19. TERMINATION OF THE INVESTIGATION**

The clinical investigation will be suspended in the event of high levels of complications and/or adverse events that are unexpected in nature and/or severity and evaluated as to causality relative to the study device. The clinical investigation may be suspended if the Medical Monitor or the IRB, upon review and evaluation of the clinical data, finds unacceptable clinical performance or the level of single or total complications and/or adverse events unacceptable for continuation of the investigation.

If causality is shown not to be related to the study device, the study may be resumed in accordance with the IRB and regulations of the FDA. The study will be terminated if causality is shown to be related to the study device.

Additionally, the investigator or JJV may stop a subject's participation at any time. JJV may also stop the study at any time for reasons it determines appropriate. However, no suspension of the study would be made to disadvantage the study subjects. Following suspension of the study for any reason, all study subjects who have already received treatment would continue to be followed through completion of the study visit schedule.

## **20. STATISTICAL METHODS**

This section highlights the analyses to be performed for key study endpoints. The key study timeframe for all endpoints will be the 1-month postoperative visit, although data will be reviewed at other time points as well. TECNIS Models ZFR00 and ZYR00 will both be compared to the TECNIS Model ZLB00 control separately for all analyses. All data will be reported by IOL group.

### **20.1 ANALYSIS POPULATION**

The safety population (SP) of all subjects implanted who have available data will be used for all analysis. No data imputation will be performed for missing data. For the monocular endpoints, the safety population will consist of first eyes implanted with a study IOL; for binocular endpoints, the safety population will consist of subjects implanted with the same IOL in both eyes. The primary analysis population will be the

safety population (SP) for all endpoints. Second eye data will only be reported for monocular safety endpoints as supportive data.

## 20.2 PRIMARY STUDY ENDPOINTS

### Primary Effectiveness Endpoints

#### MODEL ZFR00: MONOCULAR DISTANCE CORRECTED INTERMEDIATE VISUAL ACUITY (DCIVA) AT 66 CM

The primary effectiveness endpoint for the Model ZFR00 IOL is mean (LogMAR), photopic, monocular, first-eye, distance corrected intermediate visual acuity (66 cm) at 1 month postoperative. The mean, SD, median, minimum, maximum and 95% C.I. will be reported by IOL group. Results will be reported by lens group for first eyes using one-sided, two-sample t-tests with an alpha level of 0.025. Note that a lower LogMAR value is a better acuity and a higher LogMAR value is a poorer acuity. The null hypothesis is that the mean monocular DCIVA LogMAR value for the Model ZFR00 eyes is worse than or equal to that for control eyes. The alternate hypothesis is that the mean monocular DCIVA LogMAR value for Model ZFR00 eyes is better than that for control eyes.

$$H_0: \mu_c - \mu_t \leq 0 \text{ (Model ZFR00 lens is worse than (higher LogMAR) or equal to control)}$$

$$H_1: \mu_c - \mu_t > 0 \text{ (Model ZFR00 lens is better (lower LogMAR) than control)}$$

where

$\mu_t$  = mean LogMAR DCIVA for the Model ZFR00 lens

$\mu_c$  = mean LogMAR DCIVA for control lens

Reject the null hypothesis if one-sided p-value  $\leq 0.025$ .

The success criterion is a statistically significantly lower mean LogMAR value for the Model ZFR00 investigational lens compared to the control lens ( $p \leq 0.025$ ).

#### MODEL ZYR00: MONOCULAR DISTANCE CORRECTED INTERMEDIATE VISUAL ACUITY (DCIVA) AT 66 CM

The primary effectiveness endpoint for the Model ZYR00 IOL is mean (LogMAR), photopic, monocular, first-eye, distance corrected intermediate visual acuity (66 cm) at 1 month postoperative. Analysis for the Model ZYR00 will be similar to the Model ZHR00 described above. Results will be reported by lens group for first eyes using one-sided, two-sample t-tests with an alpha level of 0.025. Note that a lower LogMAR value is a better acuity and a higher LogMAR value is a poorer acuity. The null hypothesis is that the mean monocular DCIVA LogMAR value for the Model ZYR00 eyes is worse than or equal to that for control eyes. The alternate hypothesis is that the mean monocular DCIVA LogMAR value for Model ZYR00 eyes is better than that for control eyes.

$H_0: \mu_c - \mu_t \leq 0$  (Model ZYR00 lens is worse than (higher LogMAR) or equal to control)  
 $H_1: \mu_c - \mu_t > 0$  (Model ZYR00 lens is better (lower LogMAR) than control)

where

$\mu_t$  = mean LogMAR DCIVA for the Model ZYR00 lens

$\mu_c$  = mean LogMAR DCIVA for control lens

Reject the null hypothesis if one-sided p-value  $\leq 0.025$ .

The success criterion is a statistically significantly lower mean LogMAR value for the Model ZYR00 compared to the control lens ( $p \leq 0.025$ ).

### **Primary Safety Endpoints**

#### **MODEL ZFR00: RATES OF ADVERSE EVENTS VS. ISO SPE RATES**

The primary Model ZFR00 safety endpoint for this study is the rate of adverse events vs. ISO SPE rates at 1 month postoperative. The frequency and proportion of first eyes and second eyes with these events will be reported over time by IOL group. Statistical comparisons to ISO SPE rates will be based on first-eye data; adverse event rates for the Model ZFR00 investigational lens first eyes will be compared to the ISO SPE rates using a one-sided, exact test based on the binomial distribution. The null hypothesis is that the AE rate for the Model ZFR00 investigational lens eyes is lower than or equal to the ISO SPE values, and the alternative hypothesis is that the AE rate for study eyes is higher than the ISO SPE values.

$H_0: p_t \leq p_i$

$H_1: p_t > p_i$

where

$p_t$  = proportion of Model ZFR00 investigational lens eyes with the AE

$p_i$  = proportion of eyes reported in ISO SPE rates with the AE

Reject the null hypothesis if one-sided p-value  $< 0.05$ .

#### **MODEL ZYR00: RATES OF ADVERSE EVENTS VS. ISO SPE RATES**

The primary Model ZYR00 safety endpoint for this study is the rate of adverse events vs. ISO SPE rates at 1 month postoperative. The frequency and proportion of first and second eyes with these events will be reported over time by IOL group. Statistical comparisons to ISO SPE rates will be based on first-eye data; adverse event rates for Model ZYR00 investigational lens first eyes will be compared to the ISO SPE rates using a one-sided, exact test based on the binomial distribution. The null hypothesis is that the AE rate for Model ZYR00 investigational lens eyes is lower than or equal to the ISO SPE values, and the alternative hypothesis is that the AE rate for study eyes is higher than the ISO SPE values.

$$H_0: p_t \leq p_i$$

$$H_1: p_t > p_i$$

where

$p_t$  = proportion of Model ZYR00 investigational lens eyes with the AE

$p_i$  = proportion of eyes reported in ISO SPE rates with the AE

Reject the null hypothesis if one-sided p-value < 0.05.

### 20.3 ADDITIONAL ENDPOINTS

#### Intermediate Visual Acuity endpoints

Other intermediate endpoints include binocular UCIVA and DCIVA, and monocular UCIVA. For binocular UCIVA and DCIVA and monocular UCIVA, superiority approach similar to DCIVA described above will be used.

In addition, the frequency and proportion achieving each line for all other intermediate endpoints will be reported over time by IOL group.

#### Near and Distance Visual Acuity endpoints

For monocular photopic BCDVA, the frequency and proportion of eyes achieving each acuity line will be reported over time by IOL group. The proportion of investigational lens eyes achieving 20/40 or better at 1 month will be compared to the ISO SPE rate for posterior chamber IOLs (all first eyes) using a one-sided, exact test based on binomial distribution. The null hypothesis (based on the ISO guidance document) is that the proportion of investigational lens eyes achieving 20/40 or better BCDVA is greater than or equal to the ISO SPE values, and the alternative hypothesis is that the proportion of investigational lens eyes achieving 20/40 or better BCDVA is less than the ISO SPE values.

In addition, the mean logMAR photopic BCDVA will be compared between lens groups for first eyes using a non-inferiority method. The null hypothesis is that the mean difference (control minus investigational lens) between the control and investigational IOLs is  $\leq -0.1$  LogMAR (1 line) with the alternative hypothesis that the mean difference is  $> -0.1$  LogMAR. A 90% confidence interval (CI) of a two-sample, two-sided, t-test will be used for evaluation. The success criteria is achieved if the lower limit of the 90% CI of the difference is greater than  $-0.1$  LogMAR.

For monocular and binocular UCDVA, BCDVA with low contrast (10%) and binocular photopic BCDVA, similar statistics using a non-inferior method will be used. Frequency and proportion of eyes achieving each line will also be reported over time by IOL group.

For all near endpoints, a non-inferior approach similar to photopic BCDVA described above will be used. In addition, the frequency and proportion of eyes achieving each line will be reported over time by IOL group.

### **Defocus Endpoints**

For defocus results, the defocus curve will be produced by IOL group. The diopters of defocus where the mean visual acuity 20/32 or better is achieved will be derived by visual inspection of the defocus curve.

### **Manifest refraction endpoint**

Descriptive analysis of refractive sphere, cylinder and spherical equivalent (MRSE) will be reported by IOL groups for both eyes. Since refraction was performed at 4M, 0.25D will be subtracted from the sphere value. Refractive data will then be converted to plus cylinder notation.

MRSE is then calculated by the following formula:  $MRSE = \text{sphere} + \frac{1}{2} \text{cylinder}$ .

### **Questionnaire Endpoints**

For questionnaire data, including visual symptoms, the frequency and proportion of subjects with a given response will be reported by IOL group. For comparisons between IOL groups, Wilcoxon Rank-Sum test will be used for ordinal data, and Fisher's exact test will be used for categorical data. The null hypothesis is that there is no difference between responses, and the alternative hypothesis is that there is a difference between responses. Two-sided testing and alpha of 0.05 will be used to evaluate questionnaire data.

### **Safety endpoints**

For contrast sensitivity data, descriptive analyses including mean, standard deviation, median, minimum, maximum and 90% confidence intervals will be presented by IOL group.

The frequency and percentage of medical findings, lens findings and non-directed ocular/visual symptoms will be reported over time by IOL group for both eyes.

## **20.4 VISUAL ACUITY CONVENTIONS AND GENERAL STATISTICS**

Visual acuity data will be converted to LogMAR values prior to analysis and adjusted for the test distance used if it is not the standard distance for the chart. Descriptive statistics will typically include sample size (N), mean, standard deviation (SD), median, minimum (Min) and maximum (Max) as appropriate for continuous variables. For continuous variables, statistical tests (e.g., t-test) assuming normality will generally be used. For categorical data, the frequency and proportion will be reported and Fisher's

exact test or Chi-square test will generally be applied. For ordinal categorical data, the frequency and proportion will be reported with the Wilcoxon Rank-Sum test generally used.

## **20.5 INTERIM REPORTS**

Although interim study progress reports will be conducted for this study, all masking of study subjects and masked study technicians will be maintained and interim reports will not be disseminated to investigators/site personnel.

## **20.6 SAMPLE SIZE CALCULATIONS**

For the primary endpoint of distance corrected intermediate visual acuity, there is 90% power to detect a 1-line or greater difference in mean visual acuity between the investigational lens groups and the control group (assume one-sided testing with an alpha of 0.025 and standard deviation of 1.6 lines) with 65 subjects in each lens group.

For contrast sensitivity there is 80% power to detect a non-inferiority margin of 0.15 log units between the investigational lens groups and the control group (assume one-sided alpha=0.05 and standard deviation of 0.34) with 65 subjects in each lens group.

If the dropout rate is assumed at 10%, approximately 73 subjects will be implanted in each lens group to achieve a minimum of 65 subjects in each lens group at 1 and 6 months.

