### 6.3 OTHER ENDPOINTS

- Monocular and binocular, best corrected distance depth of focus
- Monocular BCDVA percent 20/40 or better vs. ISO SPE rate
- Binocular UCDVA, BCDVA, UCIVA, DCIVA, UCNVA and DCNVA
- Monocular UCDVA, UCIVA, UCNVA and DCNVA
- Monocular and binocular low-contrast BCDVA (10%)
- Monocular and binocular best corrected distance contrast sensitivity vs control (mesopic with and without glare at 1.5, 3, 6, and 12 cpd, photopic without glare at 3, 6, 12, and 18 cpd)
- Visual symptoms via PRO instrument
- Ocular/visual symptoms (non-directed responses as obtained from the open-ended question "Are you having any difficulties with your eyes or vision?")
- Subject spectacle independence and satisfaction questionnaire responses
- Medical findings/complications
- Lens findings/complications

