## APPENDIX K INSTRUCTIONS FOR CONTRAST SENSITIVITY TESTING

Contrast sensitivity testing will be measured using the M&S system for sine-wave gratings (1.5, 3, 6, 12 and/or 18 cycles per degree). Testing will be done under mesopic and mesopic with glare and photopic lighting conditions. **The test distance for the M&S system is 8 feet (2.5 meters).** Mesopic testing without glare will be performed before contrast sensitivity with glare testing.

This test is to be done monocularly at the 1-month and binocularly at the 6-month visit for all subjects. Only the first eye implanted will be tested at the 1-month visit. All subjects will be tested with best corrected manifest refraction in place, and a refraction adjustment of +0.12 D over manifest refraction in place. Subjects should be shown the contrast sensitivity target samples before dark adaptation for mesopic testing is started.

Contrast sensitivity measurements are based on subject identification of the orientation of a low contrast grating (vertical, horizontal, tilted left or tilted right). For each grating presented, the subject will have to identify or guess the orientation of the grating. After an automated protocol, contrast sensitivity values will be displayed on the laptop screen for 1.5, 3, 6, 12 and/or 18 cpd.

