7.4 CONTRAST SENSITIVITY

Contrast sensitivity testing will be performed at the 1- and 6-month visits (monocular at 1 month and binocular at 6 months). The contrast sensitivity score will be converted to log units prior to analysis (see conversion formula in Appendix II). The average of the two contrast sensitivity log scores will be used for the analysis. Analyses including mean, standard deviation, median, minimum, maximum and 90% confidence intervals will be presented by IOL group.

In addition, contrast sensitivity will also be stratified by pupil size (photopic condition using photopic pupil size ≤ 2.5 mm, > 2.5 mm to < 4.0 mm, and ≥ 4.0 mm; mesopic condition using mesopic pupil size ≤ 4.0 mm, > 4.0 mm to < 5.0 mm, and ≥ 5.0 mm) for each IOL model. For binocular testing, the average of the two pupil sizes will be used for stratification.

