8 SAMPLE SIZE CALCULATIONS

For the primary endpoint of distance corrected near visual acuity, there is 90% power to detect a 1-line or greater difference in mean visual acuity between the investigational lens groups and the control group (assume one-sided testing with an alpha of 0.025 and standard deviation of 1.6 lines) with 65 subjects in each lens group.

For contrast sensitivity, there is 80% power to detect a non-inferiority margin of 0.15 log units between the investigational lens groups and the control group (assume one-sided alpha=0.05 and standard deviation of 0.34) with 65 subjects in each lens group.

If the dropout rate is assumed at 10%, approximately 73 subjects will be implanted in each lens group to achieve a minimum of 65 subjects in each lens group at 1 and 6 months.

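### Both documents state 80% power for a contrast-sensitivity non-inferiority comparison with control, but the planned analysis gives only summaries within each lens group.

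*Protocol*

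**What the plan says.** **Power statement.** Protocol 20.6 gives two calculations. The first reads "For the primary endpoint of distance corrected intermediate visual acuity, there is 90% power to detect a 1-line or greater difference" (one-sided alpha 0.025, SD 1.6 lines). The second, for contrast sensitivity, reads "there is 80% power to detect a non-inferiority margin of 0.15 log units between the investigational lens groups and the control group" (one-sided alpha 0.05, SD 0.34). Both are tied to 65 subjects per lens group. SAP 8 repeats the second: "80% power to detect a non-inferiority margin of 0.15 log units between the investigational lens groups and the control group".

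**Endpoint list.** Protocol 6.3 lists "Monocular and binocular best corrected distance contrast sensitivity vs control" for three lighting conditions: photopic without glare, mesopic without glare and mesopic with glare. Each has four spatial frequencies.

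**Planned analysis.** Under the safety endpoints, Protocol 20.3 says: "For contrast sensitivity data, descriptive analyses including mean, standard deviation, median, minimum, maximum and 90% confidence intervals will be presented by IOL group". SAP 7.4 says: "Analyses including mean, standard deviation, median, minimum, maximum and 90% confidence intervals will be presented by IOL group", and adds pupil-size strata. SAP Appendix I lists the same summaries. None of these gives a hypothesis, an interval for the between-group difference, or any use of the 0.15 margin.

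**Timing.** Protocol 20 says: "The key study timeframe for all endpoints will be the 1-month postoperative visit". Appendix K says: "This test is to be done monocularly at the 1-month and binocularly at the 6-month visit for all subjects".

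**The concern.** A non-inferiority margin is a limit on the difference between two means. The sample-size sections fix the margin, the alpha, the SD and the comparator, yet the analysis sections never form that difference. Followed as written, the plan yields three sets of group summaries and no result that can be compared with 0.15.

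A reader could rebuild a difference interval from the reported N, mean and SD. The summaries cannot show whether 0.15 was meant to be applied, to which of the 12 conditions, or at which visit. If a comparative statement about contrast sensitivity is later made, those choices would be made with the data in view. Contrast sensitivity is listed among the additional safety endpoints, and Protocol 17 names its reduction under certain conditions as a possible risk of these lenses, so such a statement is likely to be wanted.

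**Working it through.** **Inputs.** From Protocol 20.6 and SAP 8: margin 0.15, SD 0.34, one-sided alpha 0.05, n = 65 per group. From Protocol 20.6 for the primary endpoint: 1 line, SD 1.6 lines, one-sided alpha 0.025. The true contrast-sensitivity difference behind the 80% is not stated; it is taken as 0, with other values shown in step 2.

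**1. Reproduce the stated power.** Power = P(T > t[1−alpha, 2n−2]), where T is noncentral t on 2n−2 degrees of freedom with noncentrality (margin − true deficit) / (SD × √(2/n)).
- n = 65: 0.15 / (0.34 × √(2/65)) = 0.15 / 0.0596 = 2.52; critical t (128 df) 1.657; power 0.804.
- n = 64: 0.15 / 0.0601 = 2.50; power 0.799.

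The t-test minimum for 80% is therefore 65 (64 by the normal approximation). The stated figure is correct for a single condition.

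**2. Dependence on the true difference.** At n = 65, an assumed true deficit of 0.02 gives noncentrality 0.13 / 0.0596 = 2.18 and power 0.70. A deficit of 0.05 gives 0.10 / 0.0596 = 1.68 and power 0.51.

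**3. Primary endpoint, same method.**
- n = 54: power 0.896.
- n = 55: 1 / (1.6 × √(2/55)) = 3.28; power 0.901.
- n = 65: 1 / (1.6 × √(2/65)) = 3.56; power 0.943.

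On the stated inputs the primary endpoint needs 55 per group.

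**4. What the planned intervals can show.** At n = 65 and SD 0.34, the 90% half-widths are:
- one group's mean: 1.669 × 0.34 / √65 = 0.070;
- the difference: 1.657 × 0.34 × √(2/65) = 0.099.

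With an interval for the difference, the upper limit falls below 0.15 when the observed control-minus-test difference is under 0.15 − 0.099 = 0.051. At an assumed observed SD of 0.30 or 0.40 the threshold is 0.063 or 0.034. A reader who set the limits of two group intervals against each other would in effect use 2 × 0.0704 = 0.141, giving a threshold of 0.15 − 0.141 = 0.009. The group intervals therefore cannot stand in for the missing one.

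**5. Direction.** SAP Appendix II converts scores as log10(1/contrast), so higher is better and a positive control-minus-test difference means the test lens is worse.

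**6. Number of conditions.** Three lighting conditions × four frequencies = 12 per lens at each visit: monocular, first eye, at 1 month; binocular at 6 months.

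**7. Which set is key.** The passages disagree:
- The Protocol synopsis (Data Analysis), Protocol 6 and Protocol 20 make 1 month key for all endpoints, and testing then is monocular.
- The synopsis (Evaluation Criteria) lists binocular contrast sensitivity as the additional safety endpoint, and binocular testing is done only at 6 months.
- The Nd:YAG capsulotomy text in Protocol 10.7 treats 6 months as the key examination.
- Protocol 6.3 and SAP 1 list both monocular and binocular testing.

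**The case against.** The best defence is that the general text already covers the comparison. Protocol 20 says both lenses are compared with control in all analyses. SAP 2.1 promises a table for each lens against control. Protocol 20.4 and SAP 2.3 say that tests assuming normality will generally be used. This does not fill the gap, because none of these passages supplies a margin or an interval for the difference. For best corrected distance acuity, by contrast, Protocol 20.3 and SAP 7.2 write out the hypotheses, the margin and a 90% interval of the difference. They extend that method to other distance and near acuities, but not to contrast sensitivity.

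A second defence is that the analysis is openly descriptive, in a study meant to give preliminary information for choosing a design, so no claim is at risk. That limits the seriousness. It does not explain why power is stated for a comparison that is not planned. Removing or relabelling the power sentence would also reconcile the texts, but would leave the comparison with control in Protocol 6.3 without a method.

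Three stronger readings are tempting and are not supported:

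- **That contrast sensitivity set the sample size.** On the stated inputs 65 is its minimum while the primary endpoint needs 55. But no passage says which calculation set the size, the primary endpoint alone is well covered at 65, and at one-sided 0.0125 (an alpha the documents do not state) its minimum would also be 65, with 90.1% power.
- **That the 1-month monocular results are plainly the key set.** The documents conflict, as step 7 of the working shows.
- **That 12 conditions create a stated error-rate problem.** One can calculate that with no true difference all 12 would pass with probability 0.804^12 = 7% if independent and 80% if fully correlated. Neither document contains an all-pass or any-pass rule, so these are not properties of the plan. They are only a reason to make no overall claim.

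**Conclusion.** The concern holds as an inconsistency between the sample-size and analysis sections. Both documents state power for a between-group non-inferiority comparison that neither plans to carry out. The stated 80% is arithmetically sound, but only per condition and with no true difference; it falls to about 70% or 51% if the test lens is truly 0.02 or 0.05 log units worse. The planned group intervals (half-width 0.070) do not answer the question that the difference interval (0.099) would. These figures assume SD 0.34 in both groups and 65 evaluable subjects in each.

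No primary conclusion is affected and the sample size need not change. The correction should be made before data review, because afterwards the conditions, the visit and the use of the margin could no longer be fixed independently of the results.

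**What to change.** **Protocol 20.3 and SAP 7.4, with matching rows in SAP Appendix I.** For each test lens against control, report the control-minus-test difference in mean log contrast sensitivity with a two-sided 90% t-interval. Do this for all 12 lighting-by-frequency conditions at each tested visit (monocular first eye at 1 month, binocular at 6 months). Use one table per visit and show each upper limit against 0.15. State that the condition-level results are not adjusted for multiplicity and support no overall non-inferiority claim.

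**Key set.** The sponsor should state before data review which set is key and reconcile the synopsis, Protocol 6, 10.7 and 20, and SAP 1 accordingly.

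**Protocol 20.6 and SAP 8.** State that the 80% applies per condition and assumes no true difference.

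**Cost.** Wording changes, plus 12 difference rows per lens at each of two visits, all from data already planned; no new tests or subjects. The tables become longer and the power statement looks less favourable.
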